##### 4.2.1.1 Primary Endpoint

- Safety (e.g., frequency, intensity, and relationship to study drug of serious adverse events [including unexpected deaths], change from baseline in vital sign and laboratory assessments) at Day 29

CONFIDENTIAL

This material is the property of the NYU School of Medicine and Langone Medical Center. Do not disclose or use except as authorized in writing by the study sponsor

## 4.2.2 Phase 3

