## 8.2 Classification of an Adverse Event

### 8.2.1 Severity of Event

Severity for each adverse event will be graded using the NCI Common Terminology Criteria for Adverse Events (CTCAE) system. All adverse events will be recorded:

- Grade 1: Mild; asymptomatic or mild symptoms; clinical or diagnostic observations only; intervention not indicated.
- Grade 2: Moderate; minimal, local or noninvasive intervention indicated; limiting age-appropriate instrumental activities of daily living.
- Grade 3: Severe or medically significant but not immediately life-threatening; hospitalization or prolongation of hospitalization indicated; disabling; limiting self care activities of daily living.
- Grade 4: Life-threatening consequences; urgent intervention indicated.
- Grade 5: Death related to AE.

CONFIDENTIAL

This material is the property of the NYU School of Medicine and Langone Medical Center. Do not disclose or use except as authorized in writing by the study sponsor

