#### **10.4.4.1 Adverse Events**

The Medical Dictionary for Regulatory Activities (MedDRA) dictionary will be used to classify all AEs reported during the study by system organ class (SOC) and preferred term (PT). All summary tables will include counts of patients with treatment-emergent adverse events (TEAEs). TEAEs are defined as those AEs that have an onset time either at or after the start of study drug administration and no more than 30 days after the last dose of study drug is administered. An overall summary of TEAEs will be presented with the number and percentage of patients having a TEAE, a serious TEAE, a TEAE leading to study discontinuation, a TEAE with an outcome of death, a TEAE related to study drug (definitely, probably, or possibly related), or a severe TEAE. The overall incidence of TEAEs will be summarized by SOC and by SOC and PT using the number and percentage of patients reporting an event and the number of events reported. The incidence of serious TEAEs and TEAEs leading to premature study discontinuation will be summarized in a similar manner. TEAEs will also be summarized by maximum severity (mild, moderate, or severe), and assessed relationship to study drug with the percentage of patients in each category. TEAEs leading to premature study discontinuation, and TEAEs with an outcome of death will also be presented in separate listings.

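### Adverse events are graded on five CTCAE levels but tabulated on three, with no rule for Grades 4 and 5 and an undefined count of severe events

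*Combined protocol and SAP*

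**What the plan says.** **Collection.** Section 8.2.1 (Severity of Event) states: "Severity for each adverse event will be graded using the NCI Common Terminology Criteria for Adverse Events (CTCAE) system". It defines five levels:

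- "Grade 1: Mild; asymptomatic or mild symptoms"
- "Grade 2: Moderate; minimal, local or noninvasive intervention indicated"
- "Grade 3: Severe or medically significant but not immediately life-threatening"
- "Grade 4: Life-threatening consequences; urgent intervention indicated"
- "Grade 5: Death related to AE"

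**Tabulation.** Section 10.4.4.1 (Adverse Events) states: "TEAEs will also be summarized by maximum severity (mild, moderate, or severe". Its overall summary also counts patients with a severe TEAE, without saying which grades qualify. Fatal TEAEs are counted in that summary and presented in a listing. Serious TEAEs are summarized by system organ class and preferred term.

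**Endpoint.** Section 4.2.1.1 defines the Phase 2 primary endpoint as safety, including "frequency, intensity, and relationship to study drug of serious adverse events [including unexpected deaths". Section 3.2.1 makes safety a primary objective of Phase 3 as well.

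**The concern.** The three table labels match the names of Grades 1, 2 and 3. The two highest grades have no label of their own, and the wording of Grade 3 prevents severe from being read naturally as severe or worse. Two programmers working from Section 10.4.4.1 could therefore produce different maximum-severity tables and different severe-TEAE counts from the same data.

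What is at stake is how well the plan describes intensity. The maximum-severity table and the severe-TEAE count are the only planned adverse-event summaries of intensity, and intensity is named in the Phase 2 primary endpoint. In patients hospitalized with COVID-19, the boundary between Grade 3 and Grade 4 is clinically important, and it is the boundary the planned outputs leave undefined.

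**Working it through.** The plan states no figure on this point and none needs recomputing. The check compares the collection scale with the tabulation scale, then asks whether other outputs fill the gap.

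**Step 1: match grades to rows.**

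| Grade (8.2.1) | Label in 8.2.1 | Row in 10.4.4.1 |
|---|---|---|
| 1 | Mild | Mild |
| 2 | Moderate | Moderate |
| 3 | Severe, not immediately life-threatening | Severe |
| 4 | Life-threatening | None stated |
| 5 | Death | None stated |

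Five grades are collected and three categories tabulated, so 5 − 3 = 2 grades have no matching row. No section gives a rule for collapsing them.

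**Step 2: follow the two possible readings.**

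- *Literal (severe = Grade 3).* A patient whose worst event is Grade 4 or 5 has no row. A patient with a single Grade 3 event is counted as having a severe TEAE; a patient with a single Grade 4 event is not.
- *Merged (severe = Grades 3 to 5).* Every patient has a row, but three grades share it. Deaths can be recovered from the separate count. Grades 3 and 4 cannot be separated.

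The text does not settle which reading applies, and the severe-TEAE count changes with the choice.

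**Step 3: look for the missing grades in other outputs.**

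- *Grade 5.* Fatal TEAEs are counted in the overall summary and listed (10.4.4.1), and all-cause mortality is a secondary endpoint (4.2.2.2). Fatal events are covered.
- *Grade 4.* Section 8.1.2 makes any life-threatening event serious. Such events, where treatment-emergent, therefore enter the serious-TEAE count and the system organ class and preferred term tables, which Section 10.4.4 presents by treatment group. They appear by arm, but not as a grade.
- *Can the serious-TEAE tables separate Grade 3 from Grade 4?* No. Section 8.1.2 also counts as serious an event that leads to or lengthens a hospital stay, and Section 8.2.1 includes that feature in Grade 3. Both grades can therefore fall in the same serious-TEAE row.
- *Individual listings (10.4.10).* These are patient-level data, not a comparison of arms.

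**Result.** The residual gap is Grade 4 identified by grade and by arm, together with an undefined severe-TEAE count.

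**The case against.** The strongest reply is that Section 10.4 calls its subsections brief and leaves full detail to a formal SAP, which Section 10.1 makes the final authority on analysis. That SAP's text is not in the documents supplied, and a rule that severe means Grade 3 or higher is the kind of detail it could settle. This stands in part: the SAP could close the gap. But Section 10.4.4.1 does not leave the levels open. It states three, and they do not fit the scale that Section 8.2.1 collects, so a SAP drafted from it would inherit the mismatch.

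A second reply is that a reader might infer that life-threatening events are absent from the by-arm reporting, or that a shift from Grade 3 to Grade 4 in one arm could not be noticed. The documents do not support that. These events are in the serious-TEAE tables by arm. Events such as intubation could appear there under their preferred terms, and ventilation and vasopressor use also enter the efficacy outcomes through the recovery definition, ventilation-free days and the ordinal scale. This reply stands in full and limits the point to identification by grade.

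A third reply concerns which events reach the table. Section 8.2.3 gives intubation, pressor use and resuscitated cardiac arrest as expected consequences of COVID-19, and a footnote to the Schedule of Assessments restricts collection to serious events with a reasonable possibility of a relationship to study drug. If that footnote governs, many such events may never be tabulated, however many rows there are. That is fair. Events that are tabulated would, however, tend to sit in the upper grades, where three levels discriminate least.

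Finally, collapsing to Grade 3 or higher is a workable convention. It would remove the ambiguity, though not the merging of Grades 3 and 4.

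**Conclusion.** The point holds as a reporting inconsistency. Two of five collected grades have no stated place in the maximum-severity table, and the severe-TEAE count could mean Grade 3 alone or Grade 3 and above. No planned by-arm summary identifies life-threatening events by grade.

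Its weight is small. The outputs are descriptive, and alpha, power and the primary efficacy analysis do not depend on them. Its relevance comes from the intensity component of the Phase 2 primary safety endpoint. The documents give no grade distribution, so the number of patients affected cannot be estimated.

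The conclusion assumes that no mapping exists in the unsupplied formal SAP. It also does not extend to what the DSMB will see: Sections 8.7 and 10.4.7.1 leave the scope and frequency of its reviews to a charter that is not supplied.

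**What to change.** In Section 10.4.4.1:

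1. Replace the three-level wording with maximum CTCAE grade (1, 2, 3, 4, 5).
2. In the overall summary, replace the severe-TEAE count with the number and percentage of patients with a Grade 3 or higher TEAE, and add a separate count of patients with a Grade 4 or 5 TEAE.
3. Summarize serious TEAEs by the same five grades, since the Phase 2 endpoint concerns the intensity of serious events.

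Carry the same definitions into the SAP. The cost is a short wording edit and revised table shells. The grades are already collected under Section 8.2.1, so no new data, visits or patients are needed. Stating only that severe means Grade 3 or higher would cure the ambiguity but keep Grades 3 and 4 merged; five rows add little work and avoid that loss.

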### **10.4.5 Adherence and Retention Analyses**

The number of patients enrolled and completed or discontinued will be summarized by treatment group and overall. Duration of treatment will be summarized by treatment group as the number of days the patient received randomized treatment and as a percent of the expected number of doses.

### **10.4.6 Baseline Descriptive Statistics**

Summaries of demographic and other baseline characteristic data will be presented by treatment arm for all analysis populations. For continuous measures, the mean, standard deviation, and interquartile range will be summarized. Categorical variables will be described by the proportion in each category, with the corresponding sample sizes.

### **10.4.7 Planned Interim Analysis**

#### **10.4.7.1 Safety Review**

A DSMB will be reviewing unblinded data from the study to ensure patient safety. The DSMB charter will describe the scope and frequency for regularly occurring interim safety reviews.

### **10.4.8 Additional Sub-Group Analyses**

The efficacy outcomes will be analyzed for subgroups of interest, including in the subgroup of patients co-enrolled in other trials, as specified in the SAP.

CONFIDENTIAL

### 10.4.9 Multiple Comparison/Multiplicity

This study includes a single primary endpoint. The two secondary efficacy endpoints will be tested using a strategy that preserves the overall Type I error rate.

### 10.4.10 Tabulation of Individual Response Data

Individual patient data will be listed by endpoint and time point.

### 10.4.11 Exploratory Analyses

The SAP will describe exploratory efficacy analyses.

## 10.5 Sample Size

A total sample size of approximately 400 participants (Phase 2 combined with Phase 3, or Phase 3 alone, depending on unblinding of Phase 2) randomized 1:1 using block randomization (~200 bardoxolone methyl; ~200 placebo) is expected to provide approximately 80% power at a two-sided 0.05 significance level using a generalized linear model analysis to detect a risk difference of +.14, assuming the following:

- Follow-up for events for 28 days after randomization (at Day 29)
- 2% of patients in each group drop-out prior to Day 29
- Increase in the probability of recovery from 50% for patients randomized to placebo relative to 64% of patients randomized to bardoxolone methyl.

Under these assumptions, approximately 228 (57% of the 400 enrolled) will have recovered at Day 29. The primary analysis will be based on the ITT population. The secondary endpoints will be tested using a strategy that preserves the overall Type I error rate. Analysis of the primary endpoint will occur after the last patient enrolled has been followed to Day 29. The phase 2 analysis for safety will not assess the primary endpoint and will not impact the overall type I error rate of the trial. If the DSMB concludes the trial should continue to the Phase 3 part, then the phase 2 patients will be included in the phase 3 portion of the study.

Table 5 shows effects detectable with 80% power for a total sample size of 400 and a range of proportion of placebo patients recovered at Day 29.

**Table 5. Effects detectable with 80% power for a sample size of n=400 and a range of proportion of placebo patients recovered**

Placebo Proportion Recovered at Day 29	Bardoxolone Proportion Recovered at Day 29	Risk Difference
0.350	0.488	0.14
0.400	0.539	0.14
0.450	0.590	0.14
0.500	0.638	0.14
0.550	0.686	0.14
0.600	0.732	0.13
0.650	0.776	0.13
0.700	0.819	0.12
0.750	0.861	0.11
0.800	0.900	0.10
0.850	0.936	0.09
0.900	0.969	0.07

CONFIDENTIAL

## **10.6 Measures to Minimize Bias**

### **10.6.1 Enrollment/Randomization/Masking Procedures**

An IWRS will be utilized to randomize patients 1:1 to once daily administration of bardoxolone methyl or placebo. Randomization will be performed using block randomization with the following strata: center and invasive mechanical ventilation (i.e., mechanical ventilation with endotracheal intubation) at baseline (yes or no). Enrollment of patients  $\geq 70$  years of age may be limited (e.g., comprise no more than 10% of all randomized patients), pending safety review by the DSMB and executive committee

All patients, investigators, site personnel, laboratories, and study personnel with direct involvement in the conduct of the study or their designees will be blinded to treatment assignments. To prevent potential bias, appropriate measures will be taken to ensure the blind is maintained for the patients and personnel mentioned previously. To maintain the blind, investigators will distribute blinded study drug treatment to patients as directed by the IWRS system. Investigators and patients will not be blinded to dose level, but will be blinded to treatment assignment (i.e., bardoxolone methyl vs. placebo).

An IWRS will manage treatment assignments and study drug dispensing. The only people with direct access to treatment assignments prior to database lock will be those individuals who develop and maintain the randomization code and the DSMB.

Following database lock after completion of each phase the study, randomization codes will be released to the statistical team for analysis.

### **10.6.2 Breaking the Study Blind/Participant Code**

Although bardoxolone methyl has no known antidote, under rare circumstances unblinding may be considered medically necessary.

The investigator is encouraged to contact the medical monitor to discuss situations in which he or she believes that the blind should be broken, but the investigator has the right to break the blind (e.g., in the event of a serious or life-threatening medical situation). If unblinding is required, the investigator will utilize the IWRS to perform the unblinding. If a study drug assignment is unblinded, the investigator must describe the event that required unblinding in the patient's source documents.

Patients must permanently discontinue taking study drug if their treatment assignment has been unblinded to the investigator (or designee). Such patients must undergo the same study drug discontinuation procedures as those patients who discontinue taking study drug for other reasons. Following permanent study drug discontinuation due to patient unblinding, patients should continue with study follow-up through their scheduled study assessments.

Patient treatment assignments must not be unblinded in the case of an AE or SAE, except as described above.

## **11 Source Documents and Access to Source Data/Documents**

Source data is all information, original records of clinical findings, observations, or other activities in a clinical trial necessary for the reconstruction and evaluation of the trial. Source data are contained in source documents. Examples of these original documents, and data records include: hospital records, clinical and office charts, laboratory notes, memoranda, subjects' diaries or evaluation checklists, pharmacy dispensing records, recorded data from automated instruments, copies or transcriptions certified after verification as being accurate and complete, microfiches, photographic negatives, microfilm or magnetic media, x-rays, subject files, and records kept at the pharmacy, at the laboratories, and at medico-technical departments involved in the clinical trial. It is acceptable to use CRFs as source documents.

The study case report form (CRF) is the primary data collection instrument for the study. All data requested on the CRF must be recorded, unless otherwise noted in the CRF instructions.

CONFIDENTIAL

This material is the property of the NYU School of Medicine and Langone Medical Center. Do not disclose or use except as authorized in writing by the study sponsor

Access to study records will be limited to IRB-approved members of the study team. The investigator will permit study-related monitoring, audits, and inspections by the IRB/EC, the sponsor, government regulatory bodies, and University compliance and quality assurance groups of all study related documents (e.g. source documents, regulatory documents, data collection instruments, study data etc.). The investigator will ensure the capability for inspections of applicable study-related facilities (e.g. pharmacy, diagnostic laboratory, etc.).

Participation as an investigator in this study implies acceptance of potential inspection by government regulatory authorities and applicable University compliance and quality assurance offices.

## **12 Quality Assurance and Quality Control**

QC procedures will be implemented beginning with the data entry system and data QC checks that will be run on the database will be generated. Any missing data or data anomalies will be communicated to the site(s) for clarification/resolution.

Following written SOPs, the monitors will verify that the clinical trial is conducted and data are generated, documented (recorded), and reported in compliance with the protocol, GCP, and the applicable regulatory requirements (e.g., Good Laboratory Practices (GLP), Good Manufacturing Practices (GMP)).

The investigational site will provide direct access to all trial related sites, source data/documents, and reports for the purpose of monitoring and auditing by the sponsor, and inspection by local and regulatory authorities.

## **13 Ethics/Protection of Human Subjects**

### **13.1 Ethical Standard**

This clinical study was designed and shall be implemented and reported in accordance with the ICH Harmonised Tripartite Guidelines for Good Clinical Practice, with applicable local regulations (e.g., US Code of Federal Regulations Title 21, European Directive 2001/20/EC), and with the ethical principles laid down in the Declaration of Helsinki.

The principal investigator agrees to conduct the study in accordance with the International Conference on Harmonization (ICH) for Guidance for Industry on Good Clinical Practice (GCP) ICH E6(R2) [[https://www.ich.org/fileadmin/Public\\_Web\\_Site/ICH\\_Products/Guidelines/Efficacy/E6/E6\\_R2\\_Step\\_4\\_2016\\_1109.pdf](https://www.ich.org/fileadmin/Public_Web_Site/ICH_Products/Guidelines/Efficacy/E6/E6_R2_Step_4_2016_1109.pdf)] and the principles of the Declaration of Helsinki [<https://www.wma.net/policies-post/wma-declaration-of-helsinki-ethical-principles-for-medical-research-involving-human-subjects/>]. The principal investigator must conduct all aspects of this study in accordance with all national, state, and local laws or regulations.

### **13.2 Institutional Review Board**

The protocol, informed consent form(s), recruitment materials, and all participant materials will be submitted to the IRB for review and approval. Approval of both the protocol and the consent form must be obtained before any participant is enrolled. Any amendment to the protocol will require review and approval by the IRB before the changes are implemented to the study. All changes to the consent form will be IRB approved; a determination will be made regarding whether previously consented participants need to be re-consented.

### **13.3 Informed Consent Process**

#### **13.3.1 Consent and Other Informational Documents Provided to Participants**

Because the study will be conducted under a United States Investigational New Drug Application, a signed informed consent form, in compliance with Title 21 of US CFR Part 50, will be obtained from each patient before the patient enters the study. In the event that the participant is not able to provide consent due to

CONFIDENTIAL

This material is the property of the NYU School of Medicine and Langone Medical Center. Do not disclose or use except as authorized in writing by the study sponsor

temporary loss of capacity during critical illness, the legally authorized representative will provide consent. A study team member may conduct the informed consent process via telephone or video (webex) with use of e-consent through REDCap to obtain and document informed consent from the subject or legally authorized representative.

An informed consent template may be provided by the Sponsor or designee to the investigators. The consent must be reviewed by the Sponsor or designee before IRB/EC submission. Once reviewed, the consent will be submitted by the principal investigator to his or her IRB/EC for review and approval before the start of the study. If the informed consent form is revised during the course of the study, all participants affected by the revision must sign the revised IRB/EC-approved consent form.

Before enrollment, each prospective patient or legally authorized representative will be given a full explanation of the study and be allowed to read the approved informed consent form. Once the principal investigator or designee is assured that the patient or legally authorized representative understands the implications of participating in the study, the patient will be asked to give consent to participate in the study.

Eligible patients may only be included in the study after providing IRB/EC-approved informed consent. Informed consent must be obtained before conducting any study-specific procedures (i.e., all of the procedures described in the protocol). The process of obtaining informed consent must be documented in the patient source documents.

The principal investigator or designee will provide a copy of the informed consent form (signed copy to be provided per applicable law) to the patient or legally authorized representative. The original form will be maintained in the patient's medical records at the site.

